## 2. Purpose

a) Describe the purpose for the proposed project as well as the hypotheses/research questions to be examined.

The purpose of this study is to see if using buffered lidocaine for the standard paracervical block will decrease the injection pain normally associated with the plain lidocaine solution we use as our standard protocol. Plain lidocaine is commonly used for paracervical blocks. However, some studies have suggested that buffered lidocaine may decrease the pain associated with the injection of the medication, but few studies have looked specifically at using buffered lidocaine for paracervical blocks during first trimester outpatient surgical abortions. Our hypothesis is that using buffered lidocaine for the paracervical block during first trimester surgical abortions will decrease injection pain as compared to using plain lidocaine.

b) What do the investigators hope to learn from this project?

Primary objective: To assess if buffered lidocaine reduces pain from injection more effectively than plain lidocaine for paracervical blocks during first trimester surgical abortions

Secondary objectives: To evaluate if buffered lidocaine is more effective than plain lidocaine at reducing pain during dilation and postoperative pain from first trimester surgical abortions

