A clinic staff member not involved with the conduct of the study will be trained specifically in the opening of the allocation envelopes. The clinic staff member will be trained to pull envelopes individually in a sequentially numbered order. The staff member will be trained to open the envelope and remove the study card to read the allocation group: buffered lidocaine or plain lidocaine. The staff member will be trained to not tell anyone involved in the study of the allocation assignment. The clinic staff member will then draw up the buffered lidocaine or plain lidocaine in an unlabeled syringe, and give it to the procedural physician or surgical assistant for study administration.

**Protocol Title:** Buffered Lidocaine for Paracervical Block to Decrease Injection Pain During First Trimester Surgical Abortions

**Protocol Type:** Unified IRB Form

**Date Submitted:** 01/30/2017

**Approval Period:** Draft

**Important Note:** This Print View may not reflect all comments and contingencies for approval. Please check the comments section of the online protocol. Questions that appear to not have been answered may not have been required for this submission. Please see the system application for more details.

---

All patients who consent to the study will receive standard counseling prior to their procedure. The procedure will start with a bimanual exam by the provider. Next, the provider will place a speculum, cleanse the cervix with betadine solution, and place a single-tooth tenaculum on the anterior lip of the cervix. At this point, participants assigned to Arm 1 will receive a paracervical block loaded with 20 cc of 1% lidocaine with 10 cc injected at the 4 and 8 o'clock positions of the cervicovaginal junction. Participants assigned to Arm 2 will receive a paracervical block loaded with 18 cc of 1% lidocaine and 2 cc of 8.4% sodium bicarbonate in the same fashion. The research assistant will ask the patient to verbally report their level of pain based on the 100 mm visual analog scale at the following points of the procedure:

- 1) Prior to the start of the procedure (baseline)
- 2) After speculum placement
- 3) After paracervical block
- 4) After cervical dilation
- 5) After suction curettage
- 6) Fifteen minutes postoperatively

i) Be sure to identify what procedures are experimental and what are standard of care or established practice for the condition/situation.

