**\* \* \* Background and additional procedures \* \* \***

**4. Background and additional procedures**

**a. Relevant Background: Discuss the present knowledge, appropriate literature and rationale for conducting the research. Include the rationale for the selected subject population.**

A small number of studies have addressed this research question with conflicting results.

A multiphase study was published in 1995 using various techniques of the paracervical block for surgical abortions. Using a 10 cm visual analog scale (VAS), the study found a statistically significant decrease in injection pain when using buffered lidocaine as compared to plain lidocaine and bupivacaine. However, the pain immediately after the injection decreased from 3 cm to 2 cm on the 10 cm VAS, which may not be a clinically relevant difference. Several pain studies have found that a 30% or 13-20mm difference on a 100mm VAS is clinically meaningful for patients.

Another study compared buffered lidocaine versus plain lidocaine for paracervical blocks for surgical abortions. Using an 11 point scale, the investigators found an 8% decrease in pain from injection when using buffered lidocaine versus plain lidocaine. Although this difference was statistically significant, the author concluded that this was most likely not clinically significant and thus not worth the extra cost of preparing the buffered solution.

Buffered lidocaine versus plain has been looked at in non-gynecological procedures as well. One randomized controlled study compared buffered lidocaine versus plain lidocaine for patients undergoing bilateral periocular surgery. Investigators found a 51% decrease in injection pain when using buffered lidocaine versus plain lidocaine, which was both statistically and clinically significant.

Another study compared 1% lidocaine with epinephrine versus 1% lidocaine buffered with 8.4% sodium bicarbonate for patients undergoing loop electrosurgical excision procedure (LEEP) procedure. Using a 100 mm Likert scale, the study found an eight-point decrease in procedural pain when using buffered lidocaine; however, this was not statistically significant.

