Based on previous research showing that a clinically relevant decrease in pain on a 100 mm VAS is at least 15 mm, we need to enroll 88 patients (44 in each group) to show this difference with 80% power and alpha of 0.05. Inflating this number by 10% to account for potential dropout (which is unlikely due to the lack of longitudinal follow-up), we obtain a total sample size of 98 patients (49 in each group).

Based on the typical volume of patients seen in our office practice, we anticipate that enrollment will take approximately 6-8 months.

We will assess the primary objective by comparing the mean pain score after paracervical block from participants receiving buffered

**Protocol Title:** Buffered Lidocaine for Paracervical Block to Decrease Injection Pain During First Trimester Surgical Abortions

**Protocol Type:** Unified IRB Form

**Date Submitted:** 01/30/2017

**Approval Period:** Draft

**Important Note:** This Print View may not reflect all comments and contingencies for approval. Please check the comments section of the online protocol. Questions that appear to not have been answered may not have been required for this submission. Please see the system application for more details.

---

We will assess the primary objective by comparing the mean pain score after paracervical block from participants receiving buffered lidocaine versus the mean pain score after paracervical block from participants receiving plain lidocaine. To assess our secondary objectives, we will compare the mean pain score after cervical dilation between participants assigned to Arm 1 and Arm 2 as well as compare postoperative pain between the two arms. All analyses will assume a statistical significance level of 0.05. In addition, we will monitor the extra costs of preparing buffered lidocaine solutions and how the preparation of buffered lidocaine impacts clinic flow and staffing.

c. Alternative Procedures. Describe any alternatives to participating in the research. (e.g., standard of care treatment, etc.). Any standard treatment that is being withheld must be disclosed. This information must be included in the consent form.

If a participant decides to withdraw from the study, she will receive our standard of care which is to administer a paracervical block using 20 cc of 1% plain lidocaine prior to the procedure.

d. Will subjects be followed after their active participation is complete?

N

If yes, explain why and describe how:

---

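### The primary comparison leaves out a pre-injection pain score that is already collected, and the site used in randomisation; adjusting for both is a free gain in precision

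*Combined protocol and SAP*

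**What the plan says.** Section 2 (Purpose) gives the primary objective as "To assess if buffered lidocaine reduces pain from injection more effectively than plain lidocaine". Section 3 (Procedures) sets the order of events before the injection. The speculum comes first and the cervix is then cleansed, after which the provider is to "place a single-tooth tenaculum on the anterior lip of the cervix. At this point, participants assigned to Arm 1 will receive a paracervical block". Arm 2 is treated in the same way.

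Under the same heading, "The research assistant will ask the patient to verbally report their level of pain" at six points. Item 1 is the baseline rating before the procedure starts, item 2 is "After speculum placement", and item 3 follows the block. Items 1 and 2 are therefore listed ahead of the injection in every participant. Section 3 also says that each of the two clinic locations has its own randomisation scheme.

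Section 4b sets the buffered-arm mean against "the mean pain score after paracervical block from participants receiving plain lidocaine". It mentions no covariate, no change from baseline and no term for site, and none of its analyses refers to item 1 or item 2. On size it says "we need to enroll 88 patients (44 in each group) to show this difference with 80% power and alpha of 0.05", where the difference is 15 mm, and inflates this to 98 (49 per arm) for dropout. It gives no SD.

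**The concern.** People differ in how they rate pain, and someone who scores high before an injection may also score high after it. If so, part of the spread in post-block scores can be predicted before treatment. A comparison that ignores the earlier score leaves that spread in the error term. Site is similar: allocation is balanced within location, and the analysis does not use this.

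What is at stake is the width of the interval for the treatment difference and the power at 15 mm. Bias is not at stake. Both scores and the site are known before the injection, and randomisation protects the plain comparison. The margin matters somewhat more here because no SD is stated, so the true power could be above or below target.

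**Working it through.** **Inputs.** From section 4b: difference 15 mm, 44 evaluable per arm, 80% power, alpha 0.05, 49 per arm enrolled. Assumed: two-sided test (sidedness is not stated), and correlation *r* between the pre-injection score and the post-block score (none is given, so 0 to 0.5 is shown).

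**Step 1. The plan's own figure.** It cannot be reproduced forwards without an SD, so solve backwards.
- Normal approximation: SD = 15 × √(44/2) / (1.960 + 0.842) = 70.36 / 2.802 = 25.1 mm.
- Two-sample t-test (noncentral t): SD = 24.83 mm, used below.
- Dropout: 44/0.9 = 48.9, so 49 per arm; 88/0.9 = 97.8, so 98. This agrees with the plan.

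**Step 2. Add one pain-score covariate.** Residual SD = 24.83 × √(1 − r²). Standard error = residual SD × √(2/n). Degrees of freedom fall from 2n − 2 to 2n − 3. Power comes from the noncentral t with noncentrality 15/SE, and the half-width is the 97.5% t quantile × SE.

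Example, r = 0.3, n = 49: residual SD = 24.83 × 0.954 = 23.69; SE = 23.69 × √(2/49) = 4.79; half-width = 1.985 × 4.79 = 9.50 mm; noncentrality = 15/4.79 = 3.13; power 0.873.

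| Covariate | Power, 44 per arm | Power, 49 per arm | 95% CI half-width, 49 per arm | Equivalent unadjusted n per arm, 49/(1 − r²) |
|---|---|---|---|---|
| none | 0.800 | 0.841 | 9.96 mm | 49 |
| r = 0.1 | 0.804 | 0.845 | 9.91 mm | 49.5 |
| r = 0.2 | 0.816 | 0.856 | 9.76 mm | 51.0 |
| r = 0.3 | 0.836 | 0.873 | 9.50 mm | 53.8 |
| r = 0.5 | 0.899 | 0.928 | 8.63 mm | 65.3 |

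**Step 3. The worst case.** At r = 0 the covariate only uses a degree of freedom, and the power loss is under 0.001. A two-level site term uses one more. At 49 per arm the critical value moves from 1.9850 (96 df) to 1.9855 (94 df), so even two uninformative terms cost less than 0.001. The table credits no gain to site.

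**Step 4. If the SD is not 24.8 mm.** At 49 per arm and r = 0.3 to 0.5, power goes from 0.957 to 0.971–0.989 if the SD is 20 mm, and from 0.688 to 0.728–0.808 if it is 30 mm.

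**Step 5. Why not a change score.** Its SD is SD × √(2(1 − r)), which exceeds the unadjusted SD whenever r is below 0.5. At r = 0.3 and 44 per arm, power would fall from 0.80 to 0.66. Analysis of covariance does not carry that risk.

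**The case against.** The strongest reply is that nothing here is wrong. The unadjusted comparison is valid, and on the implied SD it reaches the stated 80% power at 44 per arm and 0.84 at 49. The size of the gain depends on a correlation that the documents do not supply. At 0.1 or 0.2 it is slight, and nothing shows that a post-speculum rating correlates 0.3 or more with injection pain. All of this stands, and it is why the point is an improvement only. It is also fair to say that 4b names no test, so adjustment is not expressly ruled out; but no covariate is named, and one chosen after outcomes are seen would be open to challenge.

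A reader might infer something stronger: that because the tenaculum comes between the speculum and the block, the primary outcome is contaminated by tenaculum pain, or that item 3 fails to measure injection pain. The documents do not support either reading. Item 2 has no stated upper time limit and may be asked before or after the tenaculum. The tenaculum precedes the block in both arms. No tenaculum pain score is given anywhere, so no dilution can be estimated, and a rating moved to just after the tenaculum might add nothing over item 2. The exact wording of the item 3 question may be settled in the data collection sheet or the separate protocol file, both listed under Attachments and not among the documents available here.

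**Conclusion.** The point holds as a free gain in precision. The primary comparison uses neither pre-injection pain score nor site, although all are available for every participant at no extra effort. With 49 per arm, SD 24.8 mm and a 15 mm difference, adjusting for the pain score moves power from 0.841 to between 0.845 (r = 0.1) and 0.928 (r = 0.5), with a loss under 0.001 if the score is uninformative. The SD is inferred from the sample size under a two-sided t-test, and the correlations are assumed, so the actual gain is unknown and may be small.

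There is no bias between arms, no inflation of type I error and no shortfall against the plan's own power target on the implied SD. The result of the plan as written would be interpretable.

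**What to change.** Add one sentence to section 4b, settled before any outcome data are examined:

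> *The primary comparison is an analysis of covariance of the score after paracervical block by arm, adjusted for the post-speculum pain score (item 2) and site, two-sided 0.05.*

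Name one score only, so that the choice cannot be made after the fact. Item 2 is the later of the two and so the closer in time to the outcome. Site belongs in the model because randomisation is separate by location.

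Optionally, state in section 3 whether item 2 is asked before or after tenaculum placement. This is a clarification, and the analysis does not depend on it.

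The cost is one sentence and two degrees of freedom. No extra patients or ratings are needed, and the procedure does not change. A participant with no item 2 score would drop out of a complete-case model, so the form should be checked for that rating at the visit.

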**\* \* \* Background and additional procedures \* \* \***

**4. Background and additional procedures**

**a. Relevant Background: Discuss the present knowledge, appropriate literature and rationale for conducting the research. Include the rationale for the selected subject population.**

A small number of studies have addressed this research question with conflicting results.

A multiphase study was published in 1995 using various techniques of the paracervical block for surgical abortions. Using a 10 cm visual analog scale (VAS), the study found a statistically significant decrease in injection pain when using buffered lidocaine as compared to plain lidocaine and bupivacaine. However, the pain immediately after the injection decreased from 3 cm to 2 cm on the 10 cm VAS, which may not be a clinically relevant difference. Several pain studies have found that a 30% or 13-20mm difference on a 100mm VAS is clinically meaningful for patients.

Another study compared buffered lidocaine versus plain lidocaine for paracervical blocks for surgical abortions. Using an 11 point scale, the investigators found an 8% decrease in pain from injection when using buffered lidocaine versus plain lidocaine. Although this difference was statistically significant, the author concluded that this was most likely not clinically significant and thus not worth the extra cost of preparing the buffered solution.

Buffered lidocaine versus plain has been looked at in non-gynecological procedures as well. One randomized controlled study compared buffered lidocaine versus plain lidocaine for patients undergoing bilateral periocular surgery. Investigators found a 51% decrease in injection pain when using buffered lidocaine versus plain lidocaine, which was both statistically and clinically significant.

Another study compared 1% lidocaine with epinephrine versus 1% lidocaine buffered with 8.4% sodium bicarbonate for patients undergoing loop electrosurgical excision procedure (LEEP) procedure. Using a 100 mm Likert scale, the study found an eight-point decrease in procedural pain when using buffered lidocaine; however, this was not statistically significant.

Loma Linda University conducted a study comparing pain using 1% lidocaine with epinephrine versus 1% lidocaine with epinephrine buffered with 8.4% sodium bicarbonate for patients undergoing eyelid surgery. Using a 10 cm visual analog scale, investigators found a trend toward decreased pain from injection when using buffered lidocaine; however, this was not statistically significant.

Two studies found no difference when using buffered lidocaine versus plain lidocaine. A dental study comparing buffered lidocaine versus plain lidocaine for maxillary injections found no difference in pain with 5% buffered, 10% buffered, and nonbuffered lidocaine. Another study compared buffered versus plain lidocaine for patients undergoing incision and drainage for pulpal necrosis. No significant difference in pain was found.

Thus, very few studies have specifically looked at buffered lidocaine versus plain lidocaine for paracervical blocks during first trimester surgical abortions. The studies that have been conducted have conflicting results. Some have found benefit by reducing pain from injection or procedural pain. Other studies have found no difference in pain.

It is important to determine the ideal anesthesia for first trimester surgical abortions since it is one of the most common outpatient procedures worldwide. Buffered lidocaine for paracervical injections may have benefit for patients. However, it is more expensive to prepare and requires more planning due to a shorter shelf life. Thus, buffered lidocaine should only be used if there is a definite benefit. It is therefore important to determine if buffered lidocaine decreases injection pain during paracervical blocks for first trimester surgical abortions.

We have decided to select our study population from patients at University Women's Health Specialists offices due to the high volume of patients seeking surgical terminations of pregnancy or surgical management of miscarriages. We believe our selected patient population will reflect the diversity of Hawai'i.

**b. Describe the statistical methods of the research and plans for analysis of the data (i.e. planned statistics, justification of sample size, etc.).**

Based on previous research showing that a clinically relevant decrease in pain on a 100 mm VAS is at least 15 mm, we need to enroll 88 patients (44 in each group) to show this difference with 80% power and alpha of 0.05. Inflating this number by 10% to account for potential dropout (which is unlikely due to the lack of longitudinal follow-up), we obtain a total sample size of 98 patients (49 in each group).

Based on the typical volume of patients seen in our office practice, we anticipate that enrollment will take approximately 6-8 months.

We will assess the primary objective by comparing the mean pain score after paracervical block from participants receiving buffered

**Protocol Title:** Buffered Lidocaine for Paracervical Block to Decrease Injection Pain During First Trimester Surgical Abortions

**Protocol Type:** Unified IRB Form

**Date Submitted:** 01/30/2017

**Approval Period:** Draft

**Important Note:** This Print View may not reflect all comments and contingencies for approval. Please check the comments section of the online protocol. Questions that appear to not have been answered may not have been required for this submission. Please see the system application for more details.

---

We will assess the primary objective by comparing the mean pain score after paracervical block from participants receiving buffered lidocaine versus the mean pain score after paracervical block from participants receiving plain lidocaine. To assess our secondary objectives, we will compare the mean pain score after cervical dilation between participants assigned to Arm 1 and Arm 2 as well as compare postoperative pain between the two arms. All analyses will assume a statistical significance level of 0.05. In addition, we will monitor the extra costs of preparing buffered lidocaine solutions and how the preparation of buffered lidocaine impacts clinic flow and staffing.

c. Alternative Procedures. Describe any alternatives to participating in the research. (e.g., standard of care treatment, etc.). Any standard treatment that is being withheld must be disclosed. This information must be included in the consent form.

If a participant decides to withdraw from the study, she will receive our standard of care which is to administer a paracervical block using 20 cc of 1% plain lidocaine prior to the procedure.

d. Will subjects be followed after their active participation is complete?

N

If yes, explain why and describe how:

---

e. Will subjects have access to the study treatment/procedure after completing the study?

N

If yes, explain why and describe how:

---

f. Do any of the following apply.

i. Will subjects be audio recorded?

N

ii. Will subjects be videotaped?

N

iii. Will subjects be photographed?

N

If yes to i, ii or iii, explain the collection process and use in the context of this research of such media

---

(Explicit consent must be obtained for use of these methods for Expedited and Full Board studies.)

---

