## 3. Procedures

a) Describe in chronological order of event(s) how the activities will be conducted, providing information about all procedures (e.g. interventions/interactions with subjects, data collection, photographing, audio and video recording), including follow up procedures.

Potential participants will be identified at their office visits to the University Women's Health Specialists either at Kapi'olani or Queen's. If a patient desires surgical termination of a first trimester pregnancy or management of a failed pregnancy in the first trimester, they will first receive standard counseling and provide informed consent for the procedure. Next, the patient's eligibility for our study will be assessed. If the patient is eligible, she will be asked by a member of the research team if she is interested in participating. If she is, the study will be explained to her and written consent will be obtained after she is given the opportunity to have all of her questions answered. The patient will then complete a written questionnaire to collect demographic data.

This prospective randomized control trial will consist of two study arms. As participants are enrolled they will be randomly assigned to Arm 1, where a paracervical block will be administered with 20 cc of 1% lidocaine, which is our standard office protocol, or to Arm 2, where a paracervical block will be administered with 20 cc of 1% lidocaine buffered with 8.4% sodium bicarbonate. Patients will be randomly assigned to either Arm 1 or Arm 2 of the study. Prior to the start of the study, study assignments will be generated in a 1:1 ratio. A statistician not involved with the conduct of the study will use a computer random number generator to generate random permuted blocks. The random permuted blocks will also be randomly varied in sizes of 4, 6, & 8. This statistician will place allocation assignment cards in sequentially numbered, sealed, opaque envelopes. A different randomization scheme will be used for each location, one at the Kapi'olani office and one at the Queen's office.

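### The primary analysis adjusts for nothing, although two pain scores are taken before the injection; naming an ANCOVA in advance could add precision at almost no cost.

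*Combined protocol and SAP*

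**What the plan says.** The statistical methods are in section 4b (Background and additional procedures). The primary objective is assessed by "comparing the mean pain score after paracervical block from participants receiving buffered lidocaine versus the mean pain score after paracervical block" in the plain-lidocaine arm. For the secondary objectives the investigators will "compare the mean pain score after cervical dilation between participants assigned to Arm 1 and Arm 2" and will also compare postoperative pain. A significance level of 0.05 is given for all analyses. No test, model, covariate or baseline adjustment is named there or elsewhere in the documents supplied.

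Section 3a (Procedures) schedules six pain scores on a 100 mm VAS. The first is a baseline score before the procedure starts. The second is taken "After speculum placement". The block is given only after the speculum, the cleansing and the tenaculum, so both scores precede the study solution. The same section says "A different randomization scheme will be used for each location", which makes office a stratum of the randomisation. Neither score is given a role in the analysis, and nor is office.

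**The concern.** Pain reports differ widely between patients. Someone who reports more pain at baseline or at speculum placement may also report more pain at injection. If so, part of the spread in the post-block score can be explained before treatment begins. A comparison of raw means leaves that part in the error term. Adjusting for it would narrow the confidence interval, raise power with the same patients, and correct the estimate for the linear part of any chance imbalance in the two scores.

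Precision matters to the decision this trial is meant to inform. Section 4a puts a clinically meaningful difference at 13 to 20 mm and says buffering should be used only if its benefit is definite. A half-width near 10 mm is wide for telling a small effect from one of that size.

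The choice has to be made in advance, because a covariate model picked after the data are seen is less credible. The dilation and postoperative comparisons have the same gap.

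**Working it through.** **Inputs from section 4b.** The target rests on earlier research that "a clinically relevant decrease in pain on a 100 mm VAS is at least 15 mm". The sample of 44 per arm (88 in total) is set "to show this difference with 80% power and alpha of 0.05", then raised for 10% dropout to 49 per arm (98 in total).

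**Not in the documents, so assumed.** The test is two-sided. The SD is back-solved from the stated sample size. The multiple correlation *r* of the two pre-injection scores with the post-block score is varied from 0 to 0.6. Office is given no predictive value.

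**Step 1: the plan's own figures.** A two-sample t-test with 44 per arm, 80% power and two-sided alpha 0.05 detects a standardised difference of 0.604. The implied SD is 15 / 0.604 = 24.8 mm. With the normal approximation, SDs from 24.8 to 25.1 mm all give 44 per arm. The dropout step reproduces: 88 / 0.9 = 97.8, rounded up to 98.

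**Step 2: the planned comparison at 49 per arm.** SE = 24.83 × √(2/49) = 5.02 mm, and 15 / 5.02 = 2.99. With 96 degrees of freedom, power is 84.1%. The 95% CI half-width is 1.985 × 5.02 = 9.96 mm.

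**Step 3: ANCOVA with three covariates (two scores and office).**

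- Residual SD = 24.83 × √(1 − r²).
- Chance covariate imbalance inflates the variance by 1 + 3/(2n − 6). At n = 49 per arm this is 1 + 3/92 = 1.033.
- Degrees of freedom are 2n − 5, which is 93 at n = 49.
- Power is taken from the noncentral t distribution.

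Example at r = 0.5: residual SD = 24.83 × √0.75 = 21.50 mm; SE = 21.50 × √(2/49 × 1.033) = 4.41 mm; 15 / 4.41 = 3.40; power 92.0%; half-width 1.986 × 4.41 = 8.8 mm.

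| Analysis | Power, 49 per arm | 95% CI half-width, 49 per arm | Power, 44 per arm |
|---|---|---|---|
| Unadjusted (as planned) | 84.1% | 10.0 mm | 80.0% |
| ANCOVA, r = 0 | 82.9% | 10.1 mm | 78.5% |
| ANCOVA, r = 0.1 | 83.3% | 10.1 mm | 78.9% |
| ANCOVA, r = 0.2 | 84.4% | 9.9 mm | 80.2% |
| ANCOVA, r = 0.3 | 86.3% | 9.7 mm | 82.2% |
| ANCOVA, r = 0.5 | 92.0% | 8.8 mm | 88.8% |
| ANCOVA, r = 0.6 | 95.4% | 8.1 mm | 93.0% |

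**Step 4: break-even.** At 49 per arm, adjusted power equals unadjusted power at r = 0.147 with the two scores alone, and at r = 0.179 with office added.

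**Checks.** Simulating the ANCOVA at 49 per arm (20,000 trials per correlation) gives 83.4, 84.5, 86.3, 92.2 and 95.5% for r = 0.1, 0.2, 0.3, 0.5 and 0.6. If the test is one-sided, the implied SD is 28.1 mm, unadjusted power at 49 per arm is 83.7%, and the adjusted figures are 82.9, 83.9, 85.6, 91.0 and 94.4%. The pattern does not depend on sidedness.

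**The case against.** The strongest reply is that nothing is wrong with the plan. A comparison of means is valid under randomisation and, with an SD near 25 mm, it meets the stated power. The gain depends wholly on a correlation that the documents do not give. Cleansing and tenaculum placement also fall between the post-speculum score and the block, so that score may predict injection pain less well than hoped. All of this stands. It is why the point is an efficiency gap with a conditional benefit.

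Four narrower objections carry some weight:

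- **Cost at 44 per arm.** If dropout uses up the whole allowance and the covariates predict nothing, power falls from 80.0% to 78.5%, a little below target. That is the worst case, and it is small.
- **Missing covariates.** The model needs both pre-injection scores as well as the outcome. If three patients per arm were lost for want of a score (an assumed number), 46 per arm at r = 0.3 would give 83.9%, and the gain would vanish. Missing scores should be few in a single visit, but the plan needs a rule so that nobody is dropped.
- **Timing of the second score.** Patients are assigned as they enrol, so the post-speculum score probably follows randomisation. The solution cannot have affected it. Knowledge of the assignment could, but section 3a has the staff member keep the assignment from everyone in the study and supply an unlabelled syringe. The score is a sound covariate as long as that concealment holds.
- **Office.** These figures credit it with no benefit. The reason to include it is that the analysis should reflect the stratified randomisation.

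Section 16 also lists a separate protocol file that was not available. If it specifies an adjusted model, section 4b should say so.

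**Conclusion.** The concern holds. The plan names no covariate, although two pre-injection scores and the randomisation stratum will be on hand for the analysis. The planned analysis remains valid and unbiased. What it may give up is precision.

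The stakes are lopsided. At 49 per arm the most that adjustment can cost is 1.2 percentage points of power (84.1% to 82.9%), or 1.5 points at 44 per arm. The gain is about 2 points at r = 0.3, 8 at r = 0.5 and 11 at r = 0.6. It is material only from about r = 0.3 upward, and below about r = 0.18 there is a slight loss.

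These figures assume a two-sided test, an SD of 24.8 mm back-solved from the sample size, and an assumed range of correlations. Confidence in the size of the gain is therefore moderate. The change is worth making, but the trial does not fail without it.

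**What to change.** Replace the primary-analysis sentence in section 4b with:

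> The primary analysis is an ANCOVA of the post-block score on treatment, with the baseline and post-speculum scores and office (the randomisation stratum) as covariates; the adjusted mean difference and its 95% CI are reported.

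Use the same model for the post-dilation and 15-minute scores, and keep the raw comparison of means as supportive. Add one line on missing pre-injection scores, for example filling them with the mean over both arms combined, so that no patient with an outcome is excluded.

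A change-from-baseline analysis is not a substitute. With equal SDs its variance is 2(1 − r) times that of the raw comparison, where r is here the correlation with the baseline score alone, so it is worse than no adjustment whenever that correlation is below 0.5.

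The cost is a sentence or two of text, settled before any outcome data are seen. No new measurements or patients are needed, and the sample size can stay as it is. If the scores turn out to predict little, about one percentage point of power is lost.
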